VIII. Data Analyses. (IR-1 A priori Specific Plans for Data Analyses that Correspond to the Major Study Aims, IR-2 Assess Data Source Adequacy, IR-3 Describe Data Linkage Plans, if applicable, IR-5 Provide Sufficient Information in Reports to Allow for Assessments of the Study's Internal and External Validity, RQ-4 Identify and Assess [name]-1 Describe in Protocol Methods to Prevent and Monitor [name]-2 Use Validated Statistical Methods to Deal with Missing Data that Properly Account for Statistical Uncertainty Due to Missingness, MD-4 Examine Sensitivity of Inferences to Missing Data Methods and Assumptions, and Incorporate into Interpretation, HT-1 Examine Sensitivity of Inferences to Missing Data Methods and Assumptions, and Incorporate into Interpretation, HT-2 For all HTE Analyses, provide an analysis plan, including the use of appropriate statistical methods. HT-3 Report all Prespecified HTE Analyses and, at Minimum, the Number of Post-hoc HTE Analyses, Including All Subgroups and Outcomes Analyzed.)

Overview. All primary statistical analyses will be conducted with the intent-to-treat sample. The primary purpose of the statistical analyses is to examine and compare trends in emergency department health service utilization, posttraumatic concern severity, PTSD symptoms, and physical function longitudinally between patients in the peer-integrated collaborative care intervention and patients in the surgical team notification arms of the study. The major outcome variables are the continuous and dichotomous assessments of EDIE derived emergency department health service utilization,⁸³ patient reported posttraumatic concerns,^{69,86} PTSD symptoms (PTSD Checklist),⁹² and physical function (Medical Outcomes Study Short Form 36 (MOS SF-36).^{117,119}

The primary statistical analyses will test the hypothesis that patients randomized to the peer-integrated collaborative care intervention will demonstrate reductions in emergency department health service use when compared to patients randomized to the trauma surgery notification condition over the course of the 12-months after injury. Primary analyses will also assess whether collaborative care intervention patients demonstrate longitudinal reductions in posttraumatic concern severity and PTSD symptoms and improvements in physical function when compared to trauma surgery notification patients.

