The study team will use mixed effects regression models to test these hypotheses for both continuous and discrete outcomes.¹²⁸⁻¹³¹ The investigative group has extensive experience with this analytic approach in the analyses of longitudinal data after injury.^{20,24,47,67,68,71} In addition, these models will allow the use of covariates that model potential sources of non-response bias and time-dependent covariates. This type of model also allows the specification of random or fixed effects and the form of the serial correlation over time (if heterogeneity changes over time).

The effect of major interest will be the time by treatment group interaction term. For these models, repeated measurements of the baseline, 1-, 3-, 6-, 9-, and 12-month outcome assessments (i.e., EDIE documented emergency department utilization, concern severity, PTSD Checklist and MOS SF-36 Physical Components Summary (PCS) scale scores) will be the dependent variables. For all dependent variables, the study team will first fit models containing only time categories, intervention, and intervention by time interactions. The form of the dependent variables will determine the link function used.

The impact of including covariates in the model will be examined in planned sensitivity analyses (IR-5). As in prior study team investigation, sensitivity analyses will be used to assess the impact of key assumptions. Important injury and demographic characteristics, such as Injury Severity Score and age, will be entered into the models as covariates in planned sensitivity analyses. Prior to these analyses, the study team will examine baseline treatment group differences, using the appropriate statistics for the distribution of the variable. Although randomization should ensure balance between the two groups, it is essential to control for any known confounders in the design and analysis to prevent a biased assessment of the treatment effect. Any baseline injury, demographic, or clinical variables found to be statistically significant in this analysis will also be included as covariates in the regression models. Care processes will also be examined as part of the secondary data analytic plan.

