Standards for preventing and handling missing data (MD-1, MD-2, MD-3, MD-4, MD-5). For the primary study outcome of EDIE emergency department data for the intent-to treat sample, prior investigation documents that the study team can attain 100% patient follow-up at all-time points; therefore, for the study primary outcome, no subject missing data is anticipated. For the primary patient-reported outcomes of posttraumatic concerns, PTSD symptoms and limitations in physical function, some attrition is expected in the study sample. Prior PCORI and NIH studies by the investigative group have consistently achieved follow-up completion rates $\geq 80\%$ between 6-12 months post-injury for

patient reported outcomes.^{20,24,67,68,71,113} The study team has developed a series of methods for proactively minimizing patient attrition in follow-up that often involve patient subject informed consent prior to implementation. These methods include obtaining multiple pieces of contact information at the time of the baseline interview, maintaining contact with the patient's social network, monitoring emergency department and hospital records for evidence of new patient contact information, conducting ongoing public records searches and conducting social media searches. Due to the nature of self-report data, members of the data quality core will monitor all data entered into REDCap for missing values. Item level missing data may be able to be re-captured if identified in a timely manner. The pattern of missing data will be examined throughout the study to determine if there are patterns of non-response that could be investigated in real time.

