Missing data can contribute to biased estimations of treatment effects. Assumptions about the nature of missing data are crucial to the type of statistical analysis chosen. Full information maximum likelihood estimates from mixed effects regression models accommodate missing data that are missing at random (MAR). Missingness with MAR data allows dependence on previously observed outcome variables.¹³²⁻¹³⁴ We will use logistic regression models to determine which, if any, demographic or clinical characteristics, including treatment group membership, are predictive of subject attrition. Any factors observed to explain trends in missing data would be used as covariates in our subsequent analyses. In past studies, no sources of consistent variation to explain missing data were found.^{20,24,67,68,71,113} Based on our relatively low attrition rates and our inability to find consistent variation in past investigations, we believe that MAR is a reasonable assumption. However, we will perform a sensitivity analysis on our data using multiple imputations.¹³⁴⁻¹³⁸ All patient data including data on outcome variables will be used to estimate imputation values in replicate imputed data sets. The missing values will be filled using a Markov chain Monte Carlo algorithm for multiple imputation procedure.^{134,137,138}

Whenever patients decline participation or withdraw from the study, the study research assistant will inquire as to why the individual did not want to participate. The study team will also document when patients miss a follow-up interview but do not formally withdraw from the study. The prior study team PCORI funded investigation attained $\geq 80\%$ follow-up at each time point for patients randomized to both conditions.⁴⁷ Twenty six percent of the 171 patients were missing one or more assessments at the 1-, 3- or 6-month time point. Regression analyses that systematically assessed patterns of missing data revealed that only gender was associated with missing assessments (61% of men versus 38% of women, $P < 0.01$).

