i. Emergency Department Utilization. The primary health care system intervention target will be group differences in emergency department utilization. In the prior PCORI funded investigation, at 3-6 months post-injury, 30% of nurse notification patients versus 17% of care management patients had one or more emergency department visits (13% difference across groups), at 6-9 months post-injury, the differences were 31% nurse notification versus 21% care management (10% difference across groups), and at 12 months post-injury, the differences were 30% nurse notification

versus 22% care management (8% difference across groups).⁴⁷ With the 100% follow-up rate provided by EDIE, the probability of a 2-tailed type I error set at 5%, correlation between observations of 0.7, and a similar pattern of emergency department visits as seen in the prior PCORI investigation with 424 total patients (n = 212 in each arm), the power is ≥ 0.80 .

ii. Severity of posttraumatic concerns. In the prior PCORI investigation, at the six month post-injury time point, 74% of nurse notification patients endorsed 1 or more severe concerns versus 52% of care management patients at the six month post-injury study endpoint, for a 22% absolute difference between the two groups.⁴⁷ For patient-reported outcomes such as the endorsement of one or more severe posttraumatic concern, 20% 12-month attrition is anticipated. With 20% 12-month attrition, 424 patients, the probability of a 2-tailed type I error set at 5%, correlation between observations of 0.7 and a similar pattern of endpoint posttraumatic concern reduction as seen in the prior PCORI investigation (22% reduction in the endorsement of any severe post-injury concern), the power to detect differences in posttraumatic concern severity will be ≥ 0.80 .

iii. PTSD symptoms. In prior comparative effectiveness trials conducted by the study team, at the 12-month time point, collaborative care patients demonstrated a mean PTSD Checklist score of 37.4 (95% Confidence Interval = 34.0-40.7) and usual care patients demonstrated a mean PTSD Checklist score of 42.5 (95% Confidence Interval = 39.3-45.7).⁶⁷ Projecting these differences to the current investigation, with 20% 12-month attrition, 424 patients, the probability of a 2-tailed type I error set at 5%, correlation between observations of 0.7 and an anticipated effect size = 0.34, the power to detect differences in PTSD symptoms will be ≥ 0.80 .

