iv. Physical function. In prior comparative effectiveness trials conducted by the study team, at the 12-month time point, collaborative care patients demonstrated a mean MOS SF-36 PCS scale score of 43.7 (95% Confidence Interval = 41.0-46.5) and usual care patients demonstrated a mean MOS SF-36 score of 41.2 (95% Confidence Interval = 38.5-43.9).⁶⁷ Projecting these differences to the current investigation, with 20% 12-month attrition, 424 patients, the probability of a 2-tailed type I error set at 5%, correlation between observations of 0.7 and an anticipated effect size = 0.26, the power to detect differences in physical function will be ≥ 0.67 .

Aim 1. Additional COVID-19 Exploratory Analyses

The first step in the COVID-19 secondary analyses was to compare the baseline demographic and clinical characteristics of the pre- and post-COVID19 cohorts. The core aim of this analysis is to assess whether one impact of the pandemic has been to change the demographic, injury and clinical characteristics of study participants over time.

Next, informed in part by the RAPICE COVID-19 qualitative studies that the team had undertaken during the trial, it was decided to dichotomize the cohort into patients that did or did not have any follow-up assessment during the COVID-19 pandemic initiation in March 2020. In order to explore differential patterns of treatment response introduced by the COVID-19 pandemic, mixed effects regression models that included the 3-way interaction of treatment, by time, by COVID-19 cohort were performed. These regression models also incorporated comparisons of both intervention and control group effects, as well as isolated comparisons of pre- and post-COVID intervention group effects, at each time point.

IX. Additional Considerations Related to the Incorporation of Standards for Complex Interventions. (SCI-1 Fully

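### The only missing-data sensitivity analysis for the three patient-reported primary outcomes assumes MAR, as the primary model does, so dropout that depends on unobserved outcomes is left untested

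*Combined protocol and SAP*

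**What the plan says.** All references are to section VIII of the combined protocol and SAP.

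- **Which outcomes have missing data.** The subsection on preventing and handling missing data expects none for the EDIE emergency department outcome. It then says: "For the primary patient-reported outcomes of posttraumatic concerns, PTSD symptoms and limitations in physical function, some attrition is expected." For these outcomes, Sample Size and Power states that "20% 12-month attrition is anticipated."
- **Primary assumption.** The likelihood-based mixed models are said to handle MAR data. MAR is judged reasonable because attrition was low, and no consistent predictors of missingness were found, in past studies.
- **Sensitivity analysis.** "However, we will perform a sensitivity analysis on our data using multiple imputations." Imputed values are estimated from all patient data, outcomes included, and "The missing values will be filled using a Markov chain Monte Carlo algorithm for multiple imputation procedure." No shift, pattern or selection parameter is given.
- **Other steps.** Logistic models look for predictors of attrition, treatment group among them, and any found become covariates. Withdrawal reasons are asked for, and missing-data patterns are monitored during the study.
- **Stated aims.** The Data Analyses text says that "sensitivity analyses will be used to assess the impact of key assumptions"; the analyses it goes on to describe are covariate adjustments. The standards listed at the head of the section include MD-4, "Examine Sensitivity of Inferences to Missing Data Methods and Assumptions."

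**The concern.** Imputation from observed data varies the method but keeps the assumption. It may condition on more variables than the mixed model, and so give a somewhat different answer. It cannot detect dropout that depends on scores nobody observed. The argument for MAR has the same limit: failing to find observed predictors of missingness says nothing about dependence on unobserved values.

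Arm-specific dropout is plausible here. Patients are told their assignment. Intervention patients may have about six months of team contact and 24-hour access, while control activity is expected to end at discharge. The interview schedule is the same in both arms, but that does not make the reasons for leaving the same. Three of the four primary outcomes are exposed. Agreement between two MAR analyses could be reported as robustness without being evidence of it.

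**Working it through.** **Inputs (Sample Size and Power, and Randomization).** 212 per arm; 20% attrition, so 212 × 0.8 = 169.6, taken as 170 observed per arm; two-sided 5%. PCL 42.5 v 37.4, difference 5.1, effect size 0.34, implied SD 5.1/0.34 = 15. PCS 43.7 v 41.2, difference 2.5, "anticipated effect size = 0.26", implied SD 2.5/0.26 = 9.6. Any severe concern 74% v 52% (six-month figures).

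**Reproducing the plan.** A two-sample comparison at 12 months with 169.6 per arm gives PCS power 0.668, against the stated 0.67. PCL gives 0.879. The concern outcome, with 170 per arm, gives 0.989. The last two meet the stated bound of at least 0.80. No stated figure is disputed.

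**Tipping points.** Assume that the observed effect equals the planned one, that only intervention-arm dropouts are worse than MAR predicts, and that the SE is unchanged.

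SE = SD × √(2/n); tipping shift = (effect − 1.96 × SE) / attrition.

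| Case | n per arm | PCS shift | PCL shift |
|---|---|---|---|
| 20% attrition, completers only | 170 | (2.5 − 1.96 × 1.043)/0.2 = 2.3 points (0.24 SD) | (5.1 − 1.96 × 1.627)/0.2 = 9.6 points (0.64 SD) |
| 20% attrition, all information recovered | 212 | 3.4 points, rounding up 3.35 (0.35 SD) | 11.2 points (0.75 SD) |
| 15% attrition, completers only | 180.2 | 3.4 points (0.36 SD) | 13.4 points (0.89 SD) |
| 25% attrition, completers only | 159 | 1.6 points, rounding up 1.55 (0.16 SD) | 7.2 points (0.48 SD) |

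At n = 170, z is 2.5/1.043 = 2.40 for PCS and 5.1/1.627 = 3.13 for PCL. Bias is attrition × (intervention shift − control shift), so equal shifts with equal attrition cancel.

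**Any severe concern.** SE = √(0.74 × 0.26/170 + 0.52 × 0.48/170) = 0.051. The largest possible shift is 100 − 52 = 48 points. If every intervention dropout had a severe concern, the rate would be 0.8 × 52 + 0.2 × 100 = 61.6%, the difference 74 − 61.6 = 12.4 points, and z = 12.4/5.1 = 2.43. To lose significance, the control rate would also have to fall to 61.6 + 1.96 × 5.1 = 71.6%, which puts control dropouts at (71.6 − 0.8 × 74)/0.2 = 62%.

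**Can MAR imputation detect the problem?** A simulation of 2,000 trials assumed no true effect, SD 15, correlation 0.7 between visits and 212 per arm. All earlier visits were observed. About 20% of intervention patients were missing at month 12, with dropout depending on the unseen month-12 score; control dropout was unrelated to the score. The likelihood and imputation estimates were both biased by −0.99 points (false benefit) and correlated 0.998. Type I error under imputation was about 0.10.

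**How large might departures be?** That simulated bias corresponds to dropouts 0.99/0.20 = 4.95 points, or 4.95/15 = 0.33 SD, worse than MAR predicts. It is a severe case, with all loss at the last visit. With 20% monotone dropout spread over the visits, and dropout odds 1.3 to 2.7 times higher per SD worse current score, the departure was 0.05 to 0.19 SD. Adding an auxiliary variable correlated 0.2 to 0.4 with the outcome changed this by under 0.01 SD. All these settings are assumptions.

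**The case against.** The strongest reply is that the plan does more than run one imputation, and that little is at stake. It models attrition by treatment group, carries predictors forward, asks why patients leave, monitors patterns, and imputes from all patient data, which could include EDIE visits that remain complete after interviews stop. The references cited with the sensitivity sentence include a paper on uncertainty about the missing-data mechanism. The concern outcome cannot be tipped by one arm, PCL needs a large one-sided shift, and PCS is fragile anyway at power 0.67. The illustration uses a single 12-month contrast, while the planned effect is the time-by-treatment interaction.

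Much of this is fair on size. The safeguards make MAR more plausible, but none of them varies it. A citation does not prespecify an analysis, and the sentence that sets out the procedure names MCMC only and does not cite that paper. The plan does not state the assumption behind its imputation; MAR is inferred from the standard method. MD-4 is visible only by its title. At 20% attrition, the departures modelled with dropout spread over visits stay below the PCS tipping point of 0.24 SD. That comfort is limited: at 25% attrition PCS tips at 0.16 SD, and the severe last-visit case of 0.33 SD falls between the two 20% figures of 0.24 and 0.35 SD.

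**Conclusion.** The point holds. The plan specifies no analysis that relaxes MAR for the three patient-reported primary outcomes, and its one missing-data sensitivity analysis cannot reveal the bias that matters most. PCS is the closest call, at 2.3 to 3.4 points (0.24 to 0.35 SD) with 20% attrition. PCL is considerably more robust, at 9.6 to 11.2 points (0.64 to 0.75 SD). The concern outcome survives any one-arm shift at the planned rates.

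These sizes rest on the planned effects being observed, SDs implied by the stated effect sizes, a simple endpoint comparison, and shifts confined to intervention dropouts. They show that an assumption goes unexamined, not that any result would be wrong. The change should be made because it is cheap and could equally well show that the conclusions are robust.

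**What to change.** Keep the MCMC imputation, stating that it assumes MAR, and label it supportive. Prespecify a delta-adjusted imputation for PCL, PCS and any severe concern, with the shift varied separately in each arm over a grid fixed before unblinding. One example is 0 to 1 SD worse for PCL and PCS, and rates among dropouts from 0% to 100% for the concern outcome; the range is a choice for the trial team to justify. Report the combination of shifts, if any, at which each conclusion changes, and comment on its plausibility using the recorded withdrawal reasons.

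The cost is one paragraph in the SAP and a few extra imputation runs. No new data are needed.

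A separate editorial correction, which carries no weight above: the same subsection says that 26% of the prior trial's 171 patients missed one or more assessments, then gives 61% of men and 38% of women. An overall rate cannot lie below both subgroup rates. Since 61 + 38 = 99, the pair may be the gender split of those with missing assessments; the wording should be reconciled.

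### Do the PTSD (0.34) and physical-function (0.26) effect sizes, and the 0.67 power for physical function, need correcting?

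*Combined protocol and SAP*

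**What the plan says.** The four power statements are in Section VIII under Sample Size and Power. They are introduced as RMASS calculations whose parameters, effect sizes included, come from earlier trials by the team; three references are cited.

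Item iii (PTSD symptoms) reports, for the earlier intervention arm, that "collaborative care patients demonstrated a mean PTSD Checklist score of 37.4 (95% Confidence Interval = 34.0-40.7". The figure set against it, for the earlier control arm, is that "usual care patients demonstrated a mean PTSD Checklist score of 42.5 (95% Confidence Interval = 39.3-45.7". The item then carries the result forward, "Projecting these differences to the current investigation, with 20% 12-month attrition, 424 patients", adds a two-sided 5% error rate and a correlation of 0.7, and concludes with "an anticipated effect size = 0.34, the power to detect differences in PTSD symptoms will be ≥ 0.80".

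Item iv (physical function) has the same layout. For the intervention arm it reports that "collaborative care patients demonstrated a mean MOS SF-36 PCS scale score of 43.7 (95% Confidence Interval = 41.0-46.5". For the control arm it reports that "usual care patients demonstrated a mean MOS SF-36 score of 41.2 (95% Confidence Interval = 38.5-43.9". The attrition, sample size, error rate and correlation are those of item iii, and the item ends with "an anticipated effect size = 0.26, the power to detect differences in physical function will be ≥ 0.67". Both sets of means carry the same single citation.

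Neither item gives a standard deviation, the number of patients behind the intervals, the contrast that was powered, the assumed course of the effect over visits, or the structure of the correlation. The analysis text earlier in Section VIII says "The effect of major interest will be the time by treatment group interaction term". It treats time as categories over baseline and five follow-up visits, and it allows the form of the serial correlation to be specified later.

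**The concern.** There are two reasons to pause.

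First, each item moves directly from means and intervals to an effect size, so a reader naturally assumes that one was computed from the other. For two outcomes measured in the same arms, the confidence intervals alone fix the ratio of the standardised effects, whatever the number of patients. That ratio does not agree with 0.34/0.26, and rounding does not close the gap. If 0.34 were right on that basis, the PCS effect would be nearer 0.20 and its power lower than printed.

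Second, 0.67 is what a plain comparison of two groups at 12 months gives. The stated correlation plays no part in that, and it is not the time-by-treatment test the plan makes its main interest.

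Section VI (item d) calls PCS a primary outcome, and it is the only one of the four with stated power below 0.80. If the 0.67 were unsound, a null PCS result would be harder to interpret.

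**Working it through.** **Inputs.** From Section VIII, Sample Size and Power: two-sided 5%, 212 per arm, 20% attrition at 12 months (212 × 0.8 = 169.6 per arm), correlation 0.7, effect sizes 0.34 and 0.26, and the means and intervals quoted above.

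**1. Reproducing the stated power.** For a two-sample comparison at 12 months, power = Φ(d·√(n/2) − 1.96).

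- PCS: 0.26 × √(169.6/2) = 2.394; Φ(2.394 − 1.96) = 0.668. This matches 0.67.
- PTSD: 0.34 × √(169.6/2) = 3.131; Φ(3.131 − 1.96) = 0.879. This is consistent with ≥ 0.80.

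**2. Effect-size ratio implied by the intervals.** Take SE = (upper − lower)/3.92 in each arm.

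| | Difference | Arm SEs | SE of difference | z |
|---|---|---|---|---|
| PTSD | 42.5 − 37.4 = 5.1 | 1.709, 1.633 | 2.364 | 2.158 |
| PCS | 43.7 − 41.2 = 2.5 | 1.403, 1.378 | 1.966 | 1.271 |

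With the same arms for both outcomes, d is proportional to z, so the implied ratio is 2.158/1.271 = 1.70. Letting every mean and bound move by ±0.05 gives 1.55 to 1.86. The stated ratio is 0.34/0.26 = 1.31, or 1.26 to 1.35 with each effect size moved by ±0.005. The ranges do not overlap.

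**3. What would make both stated values right.**

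- From the mean differences alone: SD = 5.1/0.34 = 15.0 for PTSD and 2.5/0.26 = 9.6 for PCS.
- For those SDs also to match the intervals as mean ± 1.96 SE, n per arm = (SD/SE)², with SE the root mean square of the two arms: (15.0/1.671)² ≈ 81 for PTSD and (9.615/1.390)² ≈ 48 for PCS.

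So a single n with intervals of that kind cannot give both. A different n per outcome, intervals from a longitudinal model, or SDs from another source could.

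**4. Power of the planned interaction test at d = 0.26.** This is a 5-df Wald test of time category by treatment, using the noncentral chi-square. The 12-month effect is 0.26 SD and the effect is zero at baseline. Dropout is gradual, from 212 per arm at baseline to 169.6 at month 12. The effect shapes are assumptions.

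| Effect over visits | Constant correlation 0.7 | AR(1), adjacent visits 0.7 |
|---|---|---|
| Constant from month 1 | 0.942 | 0.789 |
| Linear in months | 0.879 | 0.300 |
| Linear in visit number | 0.848 | 0.286 |

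With 169.6 per arm at every visit instead, the ranges are 0.82 to 0.89 (constant) and 0.25 to 0.69 (AR(1)). Both versions assume a baseline on the same instrument, whereas Table 1 lists the SF-12 at baseline and the SF-36 only from month 1.

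**The case for a change.** The strongest case for a change is that the parallel wording, the shared citation and the reference to projecting the differences invite the reader to derive each effect size from the adjacent intervals, and that derivation fails by more than rounding. No document supplies the SD or n that would explain it. If 0.34 is taken as fixed, the PCS effect on the common basis is 0.34/1.697 = 0.20, and the 12-month power is Φ(0.20 × √84.8 − 1.96) = 0.45 instead of 0.67. The power of the planned test also ranges from about 0.3 to 0.9 over settings that the text leaves open.

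Part of this stands. The derivation is not shown, the two values were not both obtained from those intervals with one n, and the RMASS settings cannot be recovered.

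The further step, that a stated figure is wrong, does not follow. The text projects mean differences and nowhere claims to have taken its SDs from the intervals. The background review of collaborative care attributes an effect of approximately 0.34 to two earlier trials together, and Sample Size and Power credits its parameters to three references. A ratio built from one trial's intervals therefore need not test either number. The values 0.20 and 0.44 (0.26 × 1.697) hold only if the common-n premise does, and cannot be offered as corrections. Likewise, the low powers arise under AR(1), which the protocol does not mention; a single correlation between observations reads most simply as constant.

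**Conclusion.** No change to the plan follows. The interval arithmetic is correct (1.70 against 1.31), but it conflicts with the protocol only if both outcomes share one n and the SDs came from the quoted intervals, and the documents say neither. No stated figure is shown to be wrong. The 0.67 reproduces at 0.668, and with a constant correlation of 0.7 the planned test exceeds it under every effect shape tried: 0.85 to 0.94 with gradual dropout, and no lower than 0.82 with 169.6 per arm throughout. This rests on d = 0.26, the assumed shapes and a baseline on the same instrument. Under AR(1) the lower bound could fail, but nothing in the plan selects that structure.

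The gap is one of reporting: the SD, n and source behind each effect size, and the contrast and correlation structure used in RMASS. Filling it would add detail to a calculation already made. It would leave the 424 patients, the mixed model and the interaction test as they are. PCS power below 0.80 is already disclosed, the missing-data text in Section VIII treats emergency department use as the study's primary outcome, and a null PCS result would be read from its confidence interval.
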